**ANNEX 3. LIST OF ICD 9 AND ICD 10 CODES FOR COHORT CREATION**

Condition	ICD 9 codes 	ICD 10 codes 
T1DM	250.X1, 250.X3	E10.xx
T2DM	250.X0, 250.X2	E11.xx
Gestational diabetes	648.8x	O24.1x, O24.4x
Secondary diabetes	249.xx	E08.xx, E09.xx, E13.xx
Acute pancreatitis	577.0	K85.xx
Chronic pancreatitis	577.1	K86.1 Other chronic pancreatitis
Pancreatitis cancer	157.xx	C25.xx
Other disease of pancreatitis	577.2, 577.8, 577.9	K86.2, K86.3, K86.8x, K86.9

1. 2015 ICD-9-CM Diagnosis Codes: <http://www.icd9data.com/2015/Volume1/default.htm> accessed at 14 March 2020

2. 2019 ICD-10-CM Codes: <https://www.icd10data.com/ICD10CM/Codes> accessed at 14 March 2020

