- Patients with type 1 diabetes mellitus (T1DM) defined as at least 1 inpatient or outpatient International Classification of Diseases Ninth Revision, Clinical Modification (ICD-9-CM) diagnosis code of 250.x1 or 250.x3 or International Classification of Diseases, Tenth Revision, Clinical Modification (ICD-10-CM) diagnosis code of E10.x in the 6 months prior to the study drug initiation.
- Patients with secondary diabetes or gestational diabetes in the 6 months prior to the study drug initiation.
- Claims for acute or chronic pancreatitis, pancreatic cancer, or other disease of the pancreas any time prior to the study drug initiation.

Treatment line specific inclusion criteria (if feasibility assessment would allow a powered analysis) are:

- For the monotherapy cohort, patients should be new users of empagliflozin or metformin (comparator). To quantify as a new user, no use of either of the two drugs (empagliflozin or metformin) in the previous 6 months is permitted.
- For the dual therapy cohort, patients should be new users of empagliflozin (on a background of metformin) or new users of SU on a background of metformin (comparator). To quantify as a new user, no use of either of the two drugs (empagliflozin or SUs) in the previous 6 months is permitted.
- For the triple therapy cohort, patients should be new users of empagliflozin (on a background of metformin and SU) or new users of TZD on a background of metformin and SU (comparator). To quantify as a new user, no use of either of the 2 drugs (empagliflozin or TZDs) in the previous 6 months is permitted.

All codes used in cohort creation are listed in Appendix 3 and 4.

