### **9.7.7 Handling of missing values**

The absence of a code for a condition will be interpreted as an absence of the event. If a study variable is totally missing from a database, it is excluded from the analysis of the pooled data. If a variable is missing for only some of the patients a missing data category will be added and utilized in the analysis.

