6.3 STUDY POPULATION

Please see the study protocol for the details.

Codes to select study population are listed in [Annex 1](#).

One of the risk factors of acute pancreatitis is severity of diabetes and diabetes duration [[R10-6620](#), [R10-2088](#)]. In the Optum and Marketscan databases duration of diabetes can not be measured for all patients, therefore chronic use of insulin at baseline was selected as an exclusion criterion to remove severe cases of diabetes who are already at higher risk of developing acute pancreatitis. We defined 60 (or more) days of continuous exposure as chronic use of insulin for the exclusion criteria.

The operational steps are as follows:

Insulin prescriptions will be extracted during the 6 months baseline period according to insulin medication codes listed in [Annex 2](#). Despite the variations in package size and dosing schedule, a majority of insulin prescriptions are dispensed with 30 days' supply [[R21-4257](#), [R21-4258](#)].

The continuous exposure episode of insulin is constructed by linking insulin prescriptions with allowed less or equal 30 gap days [[R21-0580](#)]. If any of continuous exposure episodes have 60 or more than 60 days duration, this will be considered as chronic use of insulin and this patient will be excluded from the cohort.

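### The ICD-10 exclusion lists skip K86.0, so patients whose only recorded pancreatic history is that code may stay in a cohort meant to exclude chronic pancreatitis

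*Protocol*

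**What the plan says.** Protocol section 9.2.2 excludes patients with "Claims for acute or chronic pancreatitis, pancreatic cancer, or other disease of the pancreas any time prior to the study drug initiation". It names no exempt subtype, and the Abstract carries the same criterion.

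The code lists put this into effect. Section 9.2.2 says "All codes used in cohort creation are listed in Appendix 3 and 4", and SAP section 6.3 says "Codes to select study population are listed in" its Annex 1. In both annexes the ICD-10 entry for chronic pancreatitis is "K86.1 Other chronic pancreatitis", and the entry for other pancreatic disease is "K86.2, K86.3, K86.8x, K86.9". The ICD-9 entry for chronic pancreatitis is the bare code 577.1.

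Protocol section 9.7.7 sets the rule for a patient with no matching code: "The absence of a code for a condition will be interpreted as an absence of the event". SAP section 9.2 repeats it.

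**The concern.** The criterion is written for the whole condition, but the ICD-10 list itemises K86 and starts at .1. An entry labelled 'Other' normally sits beside a named sibling, and the code just before it is absent. An analyst who follows the annex would treat a patient known only by the omitted code as free of pancreatic disease.

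The outcome is the first acute pancreatitis event, and the exclusion exists so that counted events are incident. A retained patient with established chronic disease could bring in background or recurrent episodes unrelated to the index drug. The sample size in section 9.5 is built to rule out a ratio of 1.5 or more. If such events are spread evenly over the arms, they pull the estimate towards 1, which makes that claim easier to reach.

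**Working it through.** **Step 1. Set the criterion against the lists.** Protocol Annex 3 and SAP Annex 1 are identical on these rows.

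| Condition in the criterion | ICD-9 codes | ICD-10 codes |
|---|---|---|
| Acute pancreatitis | 577.0 | K85.xx |
| Chronic pancreatitis | 577.1 | K86.1 only |
| Pancreatic cancer | 157.xx | C25.xx |
| Other pancreatic disease | 577.2, 577.8, 577.9 | K86.2, K86.3, K86.8x, K86.9 |

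The K86 codes over all rows are .1, .2, .3, .8x and .9. K86.0 is not among them, and neither K85.xx nor K86.8x covers it. K85 and C25 are taken as whole categories; K86 is not. K86.4 to K86.7 are also unlisted. The documents do not show whether those codes exist, and a whole-category entry would settle that too.

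**Step 2. Look for a cure elsewhere.** K86.0 appears nowhere else in the readable text of either document. SAP Annex 3 lists pancreatic disease among the covariates, but a covariate removes nobody. Protocol section 9.3.3 also takes covariates from the 6 months before index, whereas the exclusion reaches back to any earlier time.

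**Step 3. Who could be retained.** Only a patient with no claim ever for any code in the table. A single listed code is enough to exclude.

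**Step 4. Illustrate the size.** The documents give no frequency for K86.0. Assume that 0.1% of the cohort carries only that code and has RR times the event rate of everyone else. Neither input has a source in the plan. The share of events from these patients is

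f = 0.001 × RR / (1 + 0.001 × (RR − 1))

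- RR = 20: 0.020 / 1.019 = 0.0196, or 2.0%
- RR = 50: 0.050 / 1.049 = 0.0477, or 4.8%

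At these levels f is close to proportional to the assumed prevalence, so half the prevalence gives about half the share.

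The planned size in section 9.5 (34,585.4 per group, rate 0.0022, one year of follow-up) implies 2 × 34,585.4 × 0.0022 = 152.2 events. The shares above are then about 3.0 and 7.3 events.

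**Step 5. Translate to the HR.** Suppose retained patients are balanced across arms and have HR 1, and the true HR in everyone else is 1.5. Let f be their share of comparator-arm events. Treating the HR as a rate ratio,

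observed HR ≈ 1.5 × (1 − f) + 1 × f = 1.5 − 0.5f

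- f = 0.0196: 1.490, a shift of 0.010
- f = 0.0477: 1.476, a shift of 0.024

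**The case against.** The omission itself is plain on the page. The case on the other side concerns certainty and size, and much of it stands.

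- **The documents never define K86.0.** The label 'Other' implies a sibling category but does not say what it holds. A reader might conclude that the ICD-10 exclusion is demonstrably narrower than the ICD-9 one. That also needs 577.1 to cover what K86.0 covers, and the annex prints only the number. It is a sound inference for the sponsor to confirm, not an established fact.
- **The leak is narrow.** A reader might infer that patients with chronic pancreatitis generally stay in. They do not: any other listed pancreatic code, at any earlier time, removes them. Secondary-diabetes codes (E08, E09, E13) in the prior 6 months also exclude.
- **Coding era.** One might infer that the arms are treated differently because the gap affects only ICD-10 history. Matching on calendar quarter, or on year as the fallback (section 9.7.2), makes era act similarly on both arms. A larger bias would need retention to differ by arm, and nothing in the documents shows that.
- **Other safeguards.** A primary case needs a lipase measurement and an abdominal ultrasound near the diagnosis (section 9.3.2). Sensitivity analyses restrict to the primary discharge diagnosis and drop K85.2x and K85.3x (section 9.7.6). Alcoholism, gallstones and pancreatic disease are listed covariates. Section 9.9.3 already concedes that some recurrent events may be counted as first events, though it blames the 6-month baseline. These limit and probe the problem without repairing the list.

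**Conclusion.** The lists do not fully implement the stated criterion, and neither document corrects this. That part rests only on reading the annexes. That K86.0 denotes a form of chronic pancreatitis is inferred from the label on K86.1 and should be checked.

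The number of patients retained cannot be worked out from the plan. Under the assumed inputs (0.1% prevalence, 20 to 50 times the risk, balance across arms, HR 1 in the retained patients) the distortion is about 0.01–0.02 at a true HR of 1.5. That is in the non-conservative direction but small. It does not by itself threaten the main conclusion. The correction is still worth making, because it removes an avoidable source of recurrent events counted as first events and brings the cohort into line with the protocol's own text.

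**What to change.** 1. Check K86.0 against the 2019 ICD-10-CM edition cited under the annex table.
2. In Protocol Annex 3 and SAP Annex 1, replace the itemised K86 codes with all K86.x codes, so that K86.0 is included. If K86.0 was left out on purpose, say so and amend the criterion in section 9.2.2 to match.
3. Rerun cohort attrition and report the patients removed by the added code, per arm and per database. If none are removed, the matter is closed.

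The cost is a code-list edit and one rerun of cohort selection, with a small loss of patients the criterion already meant to exclude. No analysis method changes.

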**ANNEX 4. MEDICATION USED TO DEFINE EXPOSURES AND EXCLUSION CRITERIA OR CENSORING**

Medication Class / Generic (Brand) Name
Medication for Exposure Groups Definition
Empagliflozin
Empagliflozin (Jardiance): Empa Mono
Empa+ Met
Metformin + Empagliflozin (Synjardy): Empa Dual
Metformin + Empagliflozin extended-release (Synjardy XR): Empa Dual
Metformin
Metformin (Glucophage, metformin hydrochloride, Fortamet, Glumetza, Riomet): Metf Mono
Met + TZD
Metformin + Pioglitazone (Actoplus Met): Metf + TZD
Metformin + Rosiglitazone (Avandamet): Metf + TZD
Met + SU
Metformin + Glipizide (Metaglip): Metformin and SU Dual
Metformin + Glyburide (Glucovance): Metformin and SU Dual
SU (Combine 1st and 2nd gen)
Glimepiride (Amaryl)
Glipizide (Glucotrol)
Glyburide (DiaBeta)
Glynase
Glycron
Micronase
Acetohexamide (Dymelor)
Chlorpropamide (Diabinese)
Tolazamide (Tolinasel)
Tolbutamide (Orinase)
TZD
Alogliptin + Pioglitazone (Oseni)
Pioglitazone (Actos)
Rosiglitazone (Avandia)
SU+ TZD
Glimepiride + Rosiglitazone (Avandaryl)
Glimepiride + Pioglitazone (Duetact)

Medicaiton used in exclusion or censoring exposure duration:
Dipeptidyl peptidase-4 inhibitor (DPP-4i)
Alogliptin (Nesina)
Metformin + Alogliptin (Kazano)
Linagliptin (Tradjenta)
Metformin + Linagliptin (Jentadueto)
Empagliflozin + Linagliptin (Glyxambi)
Saxagliptin (Onglyza)
Metformin + Saxagliptin (Kombiglyze)
Sitagliptin (Januvia)
Metformin + Sitagliptin (Janumet)
Sitagliptin + Simvastatin (Juvisync)
Glucagon-like peptide-1 receptor agonist (GLP-1 RA) with Insulin
Albiglutide (Tanzeum)
Dulaglutide (Trulicity)
Exenatide (Byetta, Bydureon)
Rybelsus (Semaglutide)
Xultophy (insulin degludec and liraglutide injection)
Glargine + Lixisenatide (Soliqua)
Liraglutide (Victoza, Saxenda)
Lixisenatide (Adlyxin)
Semaglutide (Ozempic)
Sodium-glucose cotransporter-2 inhibitors (SGLT-2i mono and combi)
Canagliflozin (Invokana)
Metformin + Canagliflozin (Invokamet)
Metformin + Canagliflozin extended-release (Invokamet XR)
Dapagliflozin (Farxiga)
Empagliflozin (Jardiance)
Empagliflozin + Linagliptin (Glyxambi)
Metformin + Empagliflozin (Synjardy)
Metformin + Empagliflozin extended-release (Synjardy XR)
Dapagliflozin + Saxagliptin (Qtem)
Metformin + Dapagliflozin extended-release (Xigduo XR)
Ertugliflozin (Steglatro)
Ertugliflozin + Metformin (Segluromet)
Ertugliflozin + Sitagliptin (Steglujan)

1. ATC codes: [https://www.who.int/ATC/DDD\\_Index/](https://www.who.int/ATC/DDD_Index/) at 31 January 2019

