#### **9.2.2 Study population**

All patients with a recorded diagnosis of T2DM who initiated empagliflozin or other oral non-incretin/non-SGLT2i-containing glucose lowering drugs (metformin, SU, or TZD) between 1 August 2014 and 31 October 2020 will be selected from the Truven MarketScan Commercial Claims and Encounters (CCAE), Truven MarketScan Medicare Supplemental (MDCR), and Optum Clininformatics® Data Mart [CDM] databases.

Comparison groups were selected based on clinical guideline recommendations and current real-world patterns of use for oral glucose lowering drugs. First-line therapy in the US and most countries according to the guidelines is metformin. SUs, TZDs, and incretin therapies are the primary non-SGLT2i alternatives for the treatment of T2DM. Several studies have reported associations between use of incretin-based medications (including dipeptidyl peptidase 4 inhibitors [DPP-4i; such as sitagliptin, saxagliptin, linagliptin, alogliptin] and glucagon-like peptide-1 receptor agonists [GLP-1 RA; such as exenatide, liraglutide, lixisenatide, dulaglutide, semaglutide] [\[P13-15588\]](#)) and risk of developing acute pancreatitis. Hence, DPP4is and GLP1RA are excluded from the comparators of this study.

Diabetes is a risk factor for acute pancreatitis [[R10-6620](#), [R10-2088](#)], but there is limited information on the duration and severity of diabetes in the US claims databases. Creating comparison groups based on treatment line might be helpful to decrease residual confounding. Therefore, to assess the risk of acute pancreatitis we decided to conduct head-to-head comparative analyses (pending feasibility assessment and adequate sample size) using the stratified therapy lines outlined below [[P17-01404](#)]:

- Monotherapy: Empagliflozin vs. metformin —> index medication is empagliflozin or metformin
- Dual therapy: Empagliflozin vs. SU (both on a background of metformin) —> index medication is empagliflozin or SU
- Triple therapy: Empagliflozin vs. TZD (both on a background of metformin plus SU) —> index medication is empagliflozin or TZD

Separate analysis of the two databases within each treatment line is the ideal approach. However, if there are not enough study participants in the Optum and MarketScan databases in each therapy line, a meta-analysis of each therapy line will be conducted between Optum and MarketScan (pending heterogeneity and sample size assessments).

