Other combinations of empagliflozin (e.g. empagliflozin on a background of SU or TZD, or empagliflozin on a background of SU and TZD) will not be assessed in this study due to the small sample size [Feasibility assessment report November 2021, data on file].

From a feasibility assessment conducted in November 2021, it is known that there are not enough study participants in the Optum and MarketScan database in each therapy line and the dual-therapy cohort was reported with the highest number of empagliflozin initiators. Therefore, a meta-analysis of the dual therapy cohorts including the data from the MarketScan MarketScan and Optum databases will be the main analysis of this study.

Due to low sample size and inadequate power, analysis of the mono- and triple therapy cohorts cannot be assessed.

Overall inclusion and exclusion criteria are listed below:

Inclusion criteria: Patients must meet all of the following criteria to be eligible for inclusion in the study:

- Patients  $\geq 18$  years old
- A diagnosis of T2DM as demonstrated by at least one qualifying diagnosis code (International Classification of Diseases (ICD)-9-CM diagnosis code of 250.x0 or 250.x2; ICD-10-CM diagnosis code of E11.x) from any encounter type recorded in the claims in the 6 months prior to the drug initiation.
- Patients initiating empagliflozin (as monotherapy, on a background of metformin, or on a background of metformin and SU) or qualifying comparator (metformin monotherapy, SU on a background of metformin, or TZD on a background of metformin and SU) during the study period.

- Have at least 6 months of continuous registration in the database prior to initiation of empagliflozin or a comparator drug

Exclusion criteria: Patients meeting any of the following criteria will be excluded from the study:

- Patients with missing or ambiguous age or sex information.
- Use of a SGLT2i, DPP-4i or GLP-1 RA in the 6 months prior to study drug initiation.
- Chronic use of insulin in the outpatient setting in the 6 months prior to the study drug initiation (definition is added to the SEAP). This criterion will help us to remove severe cases of diabetes and reduce the risk of residual confounding as diabetes is a risk factor for developing acute pancreatitis [\[R10-6620, R10-2088\]](#).

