### **9.3.1 Exposures**

For this study, eligible patients will be identified from prescriptions/dispensings for the following study medications of interest (index medications):

Study drug will include:

- New therapy with empagliflozin (index medication) for the treatment of T2DM:
  - As monotherapy
  - As dual therapy (on a background of metformin)
  - As triple therapy (on a background of metformin and SU)

Comparator will be:

- New therapy with an oral non-incretin/non-SGLT2i-containing hypoglycaemic agent for the treatment of T2DM:
  - As monotherapy (metformin monotherapy): index medication is metformin
  - As dual therapy (SU on a background of metformin): index medication is SU
  - As triple therapy (TZD on a background of metformin and SU): index medication is TZD

This leads to the following comparisons:

- Monotherapy: Empagliflozin vs metformin
- Dual therapy: Empagliflozin vs SU, both on background of metformin
- Triple therapy: Empagliflozin vs TZD, both on a background of metformin and SU

Fixed-dose combinations will be considered equivalent to their free combination regimens. For instance, initiators of Synjardy will be categorized as dual therapy of empagliflozin. Combinations beyond triple therapy (i.e., use of 4+ glucose lowering drugs) will not be considered.

The index date is defined as the date of the first recorded claim for a qualifying prescription as a new user. Patients are required to have at least 6 months of continuous registration in the database prior to initiation of empagliflozin or a comparator drug (the look-back period). The look-back period was specified to confirm new medication use (i.e., having a first prescription claim for empagliflozin or other oral non-incretin/non-SGLT2i-containing glucose lowering drugs without use in the prior 6 months) and describe baseline parameters, such as prior medical history and medications. The look-back period includes the index date.

The study will be conducted utilizing a modified “as-treated” approach. Study follow-up will start the day after initiation of index medication and will continue until:

- The first occurrence of the outcome

- The date of end of continuous registration in the database
- The date of death
- The date of study end (31 October 2020)

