\*The last date of known coverage may also be extended further to account for overlap periods – when a prescription is refilled before the previous supply was considered exhausted. Gaps between coverage and prescription refills that are less than the duration of each patient's respective grace period will be considered continuous exposure time.

#It is not typically possible to ascertain all deaths that occur in studies based on administrative claims data.

Discontinuation, addition, and switching are defined in the SEAP. Considerations for the follow up time and censoring after switching or addition are presented in Table 3.

Index drug for the monotherapy are empagliflozin and metformin, for the dual therapy empagliflozin and SU, and for the triple therapy cohort empagliflozin and TZD.

Table 3 Considerations for switching or adding during the follow-up period

Treatment Line	Index Drug	Can Add (i.e. do not censor)	Cannot Add (i.e. censor at switch/addition)
Monotherapy	Empagliflozin	SU, TZD, and medications not mentioned in the next column	Metformin, incretins*, other SGLT2i, Insulin
	Metformin	SU, TZD, and medications not mentioned in the next column	Any SGLT2i, incretins*, Insulin
Dual Therapy	Empagliflozin	TZD, and medications not mentioned in the next column	SU, incretins*, other SGLT2i, Insulin
	SU	TZD, and medications not mentioned in the next column	Any SGLT2i, incretins*, Insulin
Triple Therapy	Empagliflozin	Medications not mentioned in the next column	TZD, incretins*, other SGLT2i, Insulin
	TZD	Medications not mentioned in the next column	Any SGLT2i, incretins*, Insulin

\*Incretins = DPP-4i or GLP-1 RA.

In the dual therapy and triple therapy cohorts, if patients discontinue or switch medications other than index medication (e.g. metformin in the dual therapy cohort, and SU or metformin in the triple therapy cohort) they will not be censored; however, in the sensitivity analysis, this will be assessed by censoring those patients. Definitions for discontinuation, switch, and addition are mentioned in the SEAP.

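### Alogliptin + pioglitazone is coded only as a TZD exposure and sits in no exclusion or censoring block, contrary to the plan's own incretin rules; the effect on the main dual-therapy analysis is probably small

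*Protocol*

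**What the plan says.** Annex 4 of the protocol has two parts: products that define the exposure groups, and products used for exclusion or censoring. In the first part, under TZD, stands "Alogliptin + Pioglitazone (Oseni". In the second part, the DPP-4i block names two alogliptin products, "Alogliptin (Nesina" and "Metformin + Alogliptin (Kazano", and not the pioglitazone combination. SAP Annex 2 has the same placement.

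The text rules point the other way:

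- Protocol 9.2.2 lists alogliptin among its examples of the class: "DPP-4i; such as sitagliptin, saxagliptin, linagliptin, alogliptin".
- The same section excludes patients for "Use of a SGLT2i, DPP-4i or GLP-1 RA in the 6 months prior to study drug initiation".
- It also states the design intent: "Hence, DPP4is and GLP1RA are excluded from the comparators of this study".
- Protocol 9.3.1 says that "Fixed-dose combinations will be considered equivalent to their free combination regimens".
- Protocol 9.3.1, 9.7.1 (Tables 2 and 3) and 9.7.3 censor at the addition of an incretin-based therapy.

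In Table 3, the column of additions that do not lead to censoring reads, for both dual-therapy arms, "TZD, and medications not mentioned in the next column". Incretins are in the opposite column.

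**The concern.** The study leaves incretins out because they have been associated with acute pancreatitis, which is the outcome. Section 7 of the protocol also criticises the earlier canagliflozin study for allowing concomitant glucose-lowering treatment without restriction. A code list that admits an incretin product works against both aims.

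The lists carry weight. Protocol 9.2.2 and 9.3.1 refer to the annexes for all codes used to create the cohorts and to define exposure, and SAP 7.1.1 sends the programmer to SAP Annex 2. The lists go product by product, and nothing says that the search is by ingredient. The double programming in Protocol 9.8 would not reveal the problem, because two analysts working from the same list would agree with each other.

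At stake is incretin-exposed person-time that the text rules would remove from the main analysis. Such time could enter through prior use or through addition during follow-up.

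**Working it through.** **1. Where each DPP-4i combination is listed** (Protocol Annex 4 and SAP Annex 2 agree on these)

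| Product | DPP-4i block | SGLT2i block | Exposure list |
|---|---|---|---|
| Alogliptin + metformin | yes | no | no |
| Linagliptin + metformin | yes | no | no |
| Saxagliptin + metformin | yes | no | no |
| Sitagliptin + metformin | yes | no | no |
| Sitagliptin + simvastatin | yes | no | no |
| Empagliflozin + linagliptin | yes | yes | no |
| Dapagliflozin + saxagliptin | no | yes | no |
| Ertugliflozin + sitagliptin | no | yes | no |
| Alogliptin + pioglitazone | **no** | **no** | **TZD** |

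The lists do not follow a consistent cross-listing convention: only empagliflozin + linagliptin is entered under two classes. Every other combination is nevertheless in at least one block that excludes or censors. Alogliptin + pioglitazone is in none.

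**2. What follows in the dual-therapy cohort**

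| Event | By the text | By the lists |
|---|---|---|
| Use in the 6 months before index | DPP-4i use, so excluded | TZD use, so the DPP-4i exclusion is not triggered |
| Added during follow-up | Incretin addition, so censored | TZD addition, so follow-up continues (Table 3) |

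SAP 7.1.1 assigns the index drug in the order empagliflozin, TZD, SU, metformin. Users of the product might therefore be moved out of the SU arm but not out of the empagliflozin arm, which would make the leak uneven. This is an inference, because the figure that completes the procedure is not shown.

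**3. The plan's own design figure** (Protocol 9.5)

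Inputs: p1 = p2 = 0.0022, margin R = 1.5, one-sided alpha 0.05, power 80%, 1:1 allocation, 1 year of follow-up each. The Farrington-Manning formula with constrained maximum likelihood is

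n = (z_a√V0 + z_b√V1)² / (p2 − R·p1)²

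- Restricted estimates under the null: 0.002640 and 0.001760, which give V0 = 0.0065855.
- V1 = 0.0022 × 0.9978 × (1 + 1.5²) = 0.0071343.
- Denominator: 0.0011².
- n = (1.6449√0.0065855 + 0.8416√0.0071343)² / 0.0011² = 34,585.4 per group.

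This matches the stated 34585.4. The listing error does not change it.

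**4. Size of the leak**

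The documents give no count of users, so the share is an assumption. If a share f of one arm's person-time is on the product and the risk ratio is RR, that arm's rate is multiplied by 1 + f(RR − 1).

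| f (assumed) | RR = 2 | RR = 3 | RR = 1 |
|---|---|---|---|
| 0.1% | 1.001 | 1.002 | 1.000 |
| 0.5% | 1.005 | 1.010 | 1.000 |
| 1% | 1.010 | 1.020 | 1.000 |

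The risk ratios of 2 and 3 are the upper end of the range in the protocol's background, which runs from protective through null. With RR below 1 the factor falls below 1.

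**5. Consequence for excluding 1.5 at the stated n**

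Power = Φ{[(R·p1 − p2)√n − z_a√V0] / √V1}, with V0 and V1 recalculated for each case and a true hazard ratio of 1.

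- All in the empagliflozin arm, factor 1.01: 78.5%.
- All in the empagliflozin arm, factor 1.02: p2 = 0.002244, V0 = 0.0066512, V1 = 0.0071781, and power is Φ(0.735) = 76.9%.
- All in the SU arm, factor 1.02: the hazard ratio becomes 1/1.02 = 0.980, V0 = 0.0066512, V1 = 0.0072328, and power is Φ(0.972) = 83.5%.

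The second and third cases are the extremes of the assumed range with RR between 1 and 3. Equal use in both arms leaves the hazard ratio at 1.

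**The case against.** **The text rules may catch the product anyway.** The exclusion and censoring rules speak of DPP-4 inhibitors and incretins, and the fixed-dose rule resolves the product into its components. The abstract adds that fixed-dose combinations are considered separately for switching, addition and censoring. The annexes hold names and not drug codes, and they are not literally complete: Protocol Annex 4 has no standalone insulin entry although adding insulin censors. A programmer who searched by ingredient would find alogliptin. This stands as a reason why the leak is conditional. It does not settle which source governs, and the SAP list, which does add insulin, still omits this product.

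**Other restrictions narrow the baseline route.** Protocol 9.3.1 leaves out regimens of four or more glucose-lowering drugs, and metformin + TZD + empagliflozin is not a listed regimen. Someone on metformin and this product who then starts an index drug might drop out for those reasons, so the remaining baseline leak may be mainly use stopped before index. This partly stands. SAP 7.1.1 names only metformin and SU as the background drugs to check. The follow-up route is untouched.

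**The effect is negligible.** TZD may be added in both dual-therapy arms, so similar use would largely cancel, and a change of up to 2% in one arm is small against a margin of 1.5. This stands on size. It does not remove the conflict between list and text.

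**A stronger reading to avoid.** A reader might infer that an incretin sits in the comparator and pulls the hazard ratio down. The documents do not support that for the main analysis. TZD is an index drug only in the triple-therapy cohort, and Protocol 9.2.2 says that cohort cannot be assessed for lack of sample size and power. In the dual-therapy cohort the comparator is SU. The contamination of the comparator would arise only if the triple-therapy analysis were run after all.

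**Conclusion.** The conflict is certain. In both annexes, alogliptin + pioglitazone is an exposure product and is absent from every exclusion and censoring block, while the text treats it as incretin use. It should be corrected because the lists are the source named for the codes and the correction is easy, not because a large bias is expected.

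The consequence is conditional on programming from the lists as written. In that case the product can reach the main dual-therapy analysis through prior use and, more clearly, through addition during follow-up. Under the assumed 0.1% to 1% of one arm's person-time and a 2 to 3 fold risk, that arm's rate rises by about 0.1% to 2%. The change is zero or opposite if the incretin association is null or protective. The direction on the hazard ratio depends on which arm has more use, which the documents do not show. The sample size stays as stated.

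**What to change.** In Protocol Annex 4 and SAP Annex 2:

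1. Add alogliptin + pioglitazone to the DPP-4i block of the exclusion and censoring list.
2. Remove it from the TZD products that qualify as index medication.

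The lists and the text then agree on baseline exclusion, exposure and censoring. The cost is an edit to one product entry in each annex and the matching program code, with a negligible loss of patients and person-time if use is as rare as assumed here. A count of users by arm, taken when the code is changed, would confirm this.
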